2.2 RISK/BENEFIT ASSESSMENT

2.2.1 KNOWN POTENTIAL RISKS

Study has no Intervention.

Imaging

Structural MRI is a routine diagnostic procedure at HealthPartners, and the resting state portion merely requires 15 minutes of scan time. The patient may experience claustrophobia with the narrow imaging space, and hearing loud noises while inside the machine. A MRI scan does not involve radiation like conventional X-rays. Instead, images are generated using a magnetic field and radio signals. Because an MRI scanner uses strong magnets, subjects will be screened by the NSC Imaging staff – as for a routine MRI. People with artificial heart valve, metal plate, pin, or other metallic objects in their body (including gun shot or shrapnel) will not be eligible for this study.

Cognitive Assessments

The questions on these assessments may make participants feel uncomfortable because some parts may be easy to answer, while some parts may be difficult or tiring. It may also cause individuals to feel uncomfortable or upset.

Loss of Confidentiality

There may be a slight possibility of breach of confidential information that was collected. However, the following procedures will be implemented to reduce this risk:

- Data collection and reporting tools will be developed and stored internally.
- Data collected and stored electronically will remain confidential and secure (e.g. secured server and password protected files [REDCap]).
- Study binders will be stored in a locked file cabinet within a locked office.
- After the study is closed, all subject identifiers will be destroyed.

2.2.2 KNOWN POTENTIAL BENEFITS

No known direct benefits.

With minimal risk beyond what is typically encountered in the standard evaluation of dementia, research participants will have the opportunity to review novel rs-fMRI brain imaging that depicts the human connectome as large scale brain networks.

By employing a novel and innovative cloud-based program that is based on machine learning and HCP data, this study will serve to develop rs-fMRI as a diagnostic biomarker for DLB.

2.2.3 ASSESSMENT OF POTENTIAL RISKS AND BENEFITS

We believe the potential risks to the participants in this study are minimal. A significant portion of the study population will come from rs-fMRI from the publically accessible ADNI 2/3 database, thus reducing the number of study subjects undergoing study procedures for this project.

The following measures will be taken to protect providers and patients from the risk of breach of confidentiality:

- A unique study ID code unrelated to the medical record number or other study subject-specific information will be assigned to each patient and used to link data from various sources and needed for analysis. The study number will be used on the RedCap database and Infinitome Program. All imaging data uploaded from the NSC research site will be de-identified and uploaded to the Infinitome cloud-based server.
- Infinitome program uses an industrial grade cyber security that is superior to what is offered at the leading medical device companies. No personal health information is stored on servers and only de-identified scans are stored on a dedicated edge node on encrypted MinIO instances. Patient data is only accessed through authenticated calls from Kubernetes pods contained in the VPC. The web service requires user authentication. Only the data related to a specific facility can be retrieved through authenticated calls and are restricted to their use.

3 OBJECTIVES AND ENDPOINTS

Aim 1: Evaluate the role of rs-fMRI and connectomic analysis as a biomarker of disease in DLB using data from an ADNI-2/3 population of MCI and mild AD subjects and a clinic population of DLB subjects

Functional connectivity (FC) scores between pairs of LSBN parcellations

- Primary pairs of interest (see background for justification of these choices):
 - Locus coeruleus v. Basal nucleus of Meynert
 - Locus coeruleus v. Intralaminar nucleus of thalamus
 - Basal nucleus of Meynert v. Intralaminar nucleus of thalamus
 - PH v. FST
 - Substantia nigra v. Caudate nucleus
- Exploratory pairs: Other 15 combinations of the pre-specified parcellations, other pairs of parcellations found to be anomalies by Infinitome program

Aim 2: Correlate cross-sectional and longitudinal dysfunction between LSBN parcellations with specific neuropsychological abnormalities in DLB Patients

Functional connectivity (FC) scores between pairs of LSBN parcellations (same primary pairs of interest as Aim 1).

Scores on neuropsychological tests: WMS-R Logical Memory Story A, Boston Naming Test Short, Category Fluency, WMS-R Digit Span Forward and Backward, ANART, RAVLT, Trails A/B, WMS-R Digit Symbol, Clock Drawing, NPI-Q, FAQ, ADAS-Cog 13

4 STUDY DESIGN

4.1 OVERALL DESIGN

This is a cross-sectional study in patients with DLB with two comparison groups. The study includes analyzing resting state-functional MRI (rs-fMRI) imaging data in CN and AD subjects from the ADNI 2/3 database and in DLB subjects recruited from a multidisciplinary dementia clinic

Specific Aim #1: Evaluate the role of rs-fMRI and connectomic analysis as a diagnostic imaging biomarker for LSBN deterioration in DLB by comparing a clinic population of DLB patients with pre-existing data from an ADNI 2/3 cohort of CN and mild AD subjects

Specific Aim #2: Correlate cross-sectional dysfunction between LSBN parcellations with specific neuropsychological abnormalities in DLB patients .

4.2 OVERVIEW – STUDY PROCEDURES/DATA COLLECTION

Data will be obtained for cognitive measures and imaging data (rs-fMRI, DTI, T1) from ADNI 2/3 data base cohort subjects with AD diagnosis, CN and DLB subjects recruited from a multidisciplinary dementia clinic. See the section # for detailed study procedures/data collection. Cognitive tests were selected so as to be harmonized with those used with the ADNI-2/3 database.

This research investigation will take place at the Center for Memory and Aging at the HealthPartners Neuroscience Center (multidisciplinary dementia clinic). Potential candidates will also be referred to our site through the Park Nicollet Neurology Clinic.

4.3 END-OF-STUDY DEFINITION

A participant is considered to have completed the study if he or she has completed study visits and assessments.

5 STUDY POPULATION

For ADNI 2/3 data, we will include CN and AD subjects who have undergone rs-fMRI images (with DTI and T1 images) and have cognitive/function testing data available. Below we describe the study population regarding clinic recruitment.

5.1 INCLUSION CRITERIA

In order to be eligible to participate in this study, an individual must meet all of the following criteria:

- Age 40- 90 years
- Established DLB diagnosis (McKeith et al. 2017)
- MMSE>15

5.2 EXCLUSION CRITERIA

An individual who meets any of the following criteria will be excluded from participation in this study:

- Other forms of dementia including, but not limited to Alzheimer's dementia, frontotemporal dementia, vascular dementia, NPH, etc,
- Inability to tolerate brain fMRI
- Risk of brain fMRI due to implants or metal.

5.3 LIFESTYLE CONSIDERATIONS

NA

5.4 SCREEN FAILURES

Pre-screening Phone Call: All potential participants will undergo a pre-screening phone or a video call to determine whether they meet the inclusion/exclusion criteria. Patients will be considered ineligible if they do not meet one or more of the inclusion/exclusion criteria during pre-screening. We will collect information on why participants are ineligible or decide not to move forward with the trial.

Screen failures are defined as participants who are considered eligible during the pre-screening phone call, but it was subsequently determined that they do not meet one or more of the inclusion/exclusion criteria. We will collect information on why participants screen fail or decide not to move forward with the trial.

5.5 STRATEGIES FOR RECRUITMENT AND RETENTION

Recruitment: For Alzheimer's Disease Neuroimaging Initiative (ADNI), analysis will be based on data available from the database. As such there are no recruitment or retention activities. rs-fMRI data as well as variables listed in Table 3 & 4 will be downloaded from ADNI-2/3 for age/sex-matched mild AD (with supportive biomarkers) and age/sex-matched CN patients.

Clinic Population: Potential DLB subjects will be referred to the study coordinator by clinicians in the neurology departments of HealthPartners and Park Nicollet. Participants with clinic visits will meet with research staff. Other patients will be mailed/e-mailed a letter and flyer/brochure. An informed consent form will be provided to those individuals expressing interest in the study. A video or phone encounter will be arranged to provide additional details of the study and informed consent. This study will be listed as one of the regional DLB investigations on the Alzheimer's Association Trial Match website. All referrals will be directed to study staff who will contact interested participants by phone. Participation will include one virtual visit and two in-person visits at HealthPartners Neuroscience Center.

To reach our target enrollment, we anticipate that we will need to screen 40 people, of those 19 individuals will sign the informed consent.

Remuneration: Participants will be provided gift cards totaling \$100 per subject for completing certain visits of the research study. The gift cards will be provided at the end of the study for completing the cognitive and imaging visits.

5.6 PARTICIPANT WITHDRAWAL

5.6.1 REASONS FOR PARTICIPANT WITHDRAWAL

Participants are free to withdraw from participation in the study at any time upon request.

An investigator may withdraw a participant from the study if:

- Any medical condition, event or situation occurs such that continued participation in the study would not be in the best interest of the subject.
- The participant meets an exclusion criterion (either newly developed or not previously recognized) that precludes further study participation.
- Significant study procedure non-compliance
- Lost-to-follow up; unable to contact subject

5.6.2 HANDLING OF PARTICIPANT WITHDRAWALS

The reason for participant discontinuation or withdrawal from the study will be recorded on the relevant eCRF. Subjects who sign the informed consent form and undergo only cognitive measures, and not imaging will not have completed participation and may be replaced.

A participant will be considered lost to follow-up if he or she fails to attend any scheduled study visit and study staff are unable to contact the participant after at least 5 attempts.

The following actions must be taken if a participant fails to attend any required study visit:

- Study staff will attempt to contact the participant, reschedule the missed visit, counsel the participant on the importance of maintaining the assigned visit schedule and ascertain if the participant wishes to and/or should continue in the study.
- Before a participant is deemed lost to follow-up, the investigator or designee will make every effort to regain contact with the participant (where possible, telephone calls or e-mail – if no answer leave a voicemail on the first and last attempt). These contact attempts will be documented.
- Should the participant continue to be unreachable, he or she will be considered to have withdrawn from the study with a primary reason of lost to follow-up.

6 STUDY SCHEDULE

The sections below are only for recruitment of DLB patients for clinic. See Section 11.1 for schedule.

6.1 SCREENING

6.1.1 SCREENING/CONSENT VISIT (VISIT 1) (DAY 0)

- This visit may be a telephone/video visit
- Review, obtain and document consent from subject and caregiver (e-consent)
- Administer MMSE
- Review medical history, demographics to determine eligibility to participate
- Review history regarding any contraindications for MRI imaging
- Schedule study visits for individuals who are eligible and available for the duration of the study

- A total time of 40 minutes is anticipated for this visit

6.2 COGNITIVE VISIT (VISIT 2) (WITHIN 3 WEEKS OF VISIT 1)

- Verify inclusion/exclusion criteria
- Neuropsychological battery as mentioned in Section 7.
- Schedule Imaging visit if not scheduled
- This visit may be combined with imaging visit, but imaging can be performed only after cognitive assessments
- This visit is at the clinic (HealthPartners Neuroscience Center [NSC]), is about 60 minutes.

6.3 IMAGING VISIT (VISIT 3 – AT NSC) (WITHIN 3 WEEKS OF VISIT 2)

- Verify inclusion/exclusion criteria
- Subject will undergo MRI imaging as mentioned in Section 7.
- This visit may be combined with cognitive visit, but imaging can be performed only after cognitive assessments
- This visit is at the clinic (NSC), is about 50 minutes.

6.4 OPTIONAL RESULTS REVIEW VISIT (AFTER VISIT 3 – AT NSC/VIRTUAL)

An optional 30 minute visit may be scheduled to share the brain imaging results with the subject and the caregiver by the PI. The participant can decide whether or not they would like to attend this visit, which can either be virtual or at NSC.

Participants will be asked to adhere to study visits and to complete study assessments. Participants will remain active unless withdrawn from the study. These will be documented in the relevant CRF.

7 STUDY ASSESSMENTS AND PROCEDURES

7.1 STUDY ASSESSMENTS FOR ENROLLED PATIENTS

7.1.1 DEMOGRAPHICS AND MEDICAL HISTORY

Demographic information will be collected, including: gender, age, race, ethnicity, height, weight, BMI, education, dementia diagnosis, co-morbidities (such as Diabetes, Hypertension) and e-mail address for consent.

7.1.2 MMSE (MINI-MENTAL STATUS EXAMINATION)

Originally developed in 1976 by Folstein, the MMSE is a paper-based test commonly used in clinical and research settings (Folstein, Folstein, & McHugh, 1975). A 30 point cognitive screening tool that assesses orientation, working memory, short term memory, visuospatial construction, and language.

7.1.3 NEUROPSYCHOLOGICAL ASSESSMENTS

All enrolled subjects will undergo the following cognitive scales. These will be administered by the research staff trained in these assessments using instructions specific for tests under the guidance/supervision of the study neuropsychologist. Cognitive tests (validated) were selected so as to be harmonized with those used with the ADNI-2/3 database. Testing will take between 45-60 min. The following battery will be administered:

Table 3. Neuropsychological Battery (Visit 2)

Cognitive Test/Scale	Domain	References
WMS R Logical Memory Story A	Story Memory/Delay	(Wechsler, 1987)
ADAS-COG-13 Number Cancellation	Visual Attention	(Rosen, Mohs, & Davis, 1984)
ADAS-COG—13 Praxis	Visuoconstruction	(Rosen et al., 1984)
Boston Naming Test (Odd items)	Naming	(Kaplan, Goodglass, & Weintraub, 1983)
Verbal Fluency	Verbal Fluency	(Butters, Granholm, Salmon, Grant, & Wolfe, 1987)
WMS R Digit span F and B	Auditory Attention	(Wechsler, 1987)
ANART	Pre-morbid function	(Nelson & O'Connell, 1978)
RAVLT	List Learning/Memory/Recog	(Rey, 1964; Rosenberg, Ryan, & Prifitera, 1984)
Trails A/B	Attention/Executive Function	(Reitan, 1958)
Clock Drawing	Clock Draw	(Goodglass & Kaplan, 1983)
NPI-Q	Neuropsychiatric Symptom	(Kaufer et al., 2000)
FAQ	Functional assessment	(Pfeffer, Kurosaki, Harrah Jr, Chance, & Filos, 1982)

ADAS-Cog-13=Alzheimer's Disease Assessment Scale-cognitive subscale 13; WMS R=Weschler Memory Scale-Revised; ANART=American National Adult Reading Test; RAVLT: Rey Auditory Verbal Learning Test; Rey O Copy: Rey Osterrieth Figure Copy; NPI-Q: Neuropsychiatric Inventory Questionnaire; FAQ: Functional Assessment Questionnaire

7.1.4 MRI IMAGING

Subjects will undergo MRI imaging at HealthPartners Neuroscience Center. Subjects will be screened for any contraindications for MRI. Subjects will undergo a protocol based on recommendation by Omniscent (o8t MR Acquisition Recommendations). We anticipate 15 minutes of scan run time using a 3T Siemens Skyra scanner and the following images will be obtained.

- 1) High-resolution multi-scan directional diffusion scan, which is most similar to a diffusion tensor image (DTI) acquisition - Specifically, diffusion weighted imaging with the following acquisition parameters will be used: *2 mm x 2 mm x 2 mm voxels, FOV = 25.6 cm, matrix = 128 mm x 128 mm, slice thickness = 2.0 mm, one non-zero b-value of b = 1000, 40 directions, and gap = 0.0 mm.*

- 2) EPI BOLD rs-fMRI - A resting-state fMRI as a T2-star EPI sequence, with 3 x 3 x 3-mm voxels, 128 volumes/run, a TE = 27ms, a TR = 2.8s, a field of view – 256mm, a flip angle = 90°
- 3) Anatomical Scan –T1 Weighting

All images will be de-identified and uploaded to the infinitome cloud-based server to be analyzed. Internal guidelines/best practices based on infinitome user manual will be developed for transfer, obtaining accounts, uploading of raw images and downloading of analyzed data.

7.1.5 CONNECTOMIC ANALYSIS

All subject images will be processed using the infinitome tool. This tool creates a machine learning-based, subject specific version of the Human Connectome Project-Multimodal Parcellation (HCP-MMP1) atlas based upon diffusion tractography structural connectivity. This will be used to conduct a connectomic analysis to identify large scale brain networks.

7.2 ADNI DATABASE

A data use agreement with ADNI will be completed prior to downloading the data for analysis from the ADNI database (ADNI Database). A user login – for research staff will be used for downloading the data.

All necessary ADNI data for MCI, mild AD patients, and cognitively normal (CN) will be downloaded to a local secure server for further analysis.

Data will be obtained regarding demographics, medical history, cognitive assessments (as mentioned in earlier sections), MMSE for eligibility, biomarkers and imaging (as mentioned in the previous section). The imaging data will be uploaded and processed with the Infinitome software as stated in the previous sections.

7.3 UNANTICIPATED PROBLEMS

7.3.1 DEFINITION OF UNANTICIPATED PROBLEMS

This protocol uses the definition of Unanticipated Problems as defined by the Office for Human Research Protections (OHRP). OHRP considers unanticipated problems involving risks to participants or others to include, in general, any incident, experience, or outcome that meets **all** of the following criteria:

1. Unexpected in terms of nature, severity, or frequency given (a) the research procedures that are described in the protocol-related documents, such as the IRB-approved research protocol and informed consent document; and (b) the characteristics of the participant population being studied;
2. Related or possibly related to participation in the research (“possibly related” means there is a reasonable possibility that the incident, experience, or outcome may have been caused by the procedures involved in the research); and

3. Suggests that the research places participants or others at a greater risk of harm (including physical, psychological, economic, or social harm) than was previously known or recognized.

7.3.2 UNANTICIPATED PROBLEMS REPORTING

The PI will report unanticipated problems (UPs) to the reviewing IRB. The UP report will include the following information:

- Protocol identifying information: protocol title and number, PI's name, and the IRB project number
- A detailed description of the event, incident, experience, or outcome
- An explanation of the basis for determining that the event, incident, experience, or outcome represents an UP
- A description of any changes to the protocol or other corrective actions that have been taken or are proposed in response to the UP

To satisfy the requirement for prompt reporting, UPs will be reported using the following timeline:

- UPs will be reported to the IRB as soon as possible, but no later than 10 working days after the investigator first learns of the event

7.3.3 REPORTING UNANTICIPATED PROBLEMS TO PARTICIPANTS

Following IRB review of any unanticipated problems, the PI will follow the IRB's recommended actions. This may include, but is not limited to, modifying the informed consent document or process, re-consenting current participants, providing information to past or current participants (e.g. whenever the information may relate to the participant's willingness to continue participants), and modifications to the protocol/research plan.

8 STATISTICAL CONSIDERATIONS

8.1 STATISTICAL ANALYSIS PLAN

Preliminary data analysis: One-way ANOVA will be used to compare demographic and baseline clinical characteristics across groups. **no missing data expected, SAS, p-value

Aim 1 Analysis: For the between-group analysis of functional connectivity, general linear model multivariate analysis of variance will be used with FC values between pairs of LSBN parcellations as dependent variables and group (DLB, AD, and CN) as a factor variable. Bonferroni post hoc test will be used to correct for multiple comparisons. The primary pairs of interest (see **Table 4**) based on available literature (see background and **Table 2**) will be analyzed first. Other combinations of these seven parcellations will be analyzed secondarily. If additional, unexpected anomalies are present between groups, we will test them in an exploratory fashion to advance this novel field of study.

Aim 2 Analysis: Pearson correlation analyses will be performed between functional connectivity values and neuropsychological test scores to evaluate the relationship between connectivity strengths and the clinical phenotype of DLB. Similar to Aim 1, we will focus on pre-specified pairs of interest, but will explore others if they present themselves in the functional connectivity analysis.

Table 4: Data Variables
Population Descriptors: age, sex, race, ethnicity, education, measures of baseline cognition (e.g. MoCA)
Aim 1: Evaluate the role of rs-fMRI and connectomic analysis as a biomarker of disease in DLB using data from an ADNI-2/3 population of MCI and mild AD subjects and a clinic population of DLB subjects
Group variable: DLB, AD, or CN

Dependent variables: Functional connectivity (FC) scores between pairs of LSBN parcellations
 
 • Primary pairs of interest (see background for justification of these choices): 
 ○ Locus coeruleus v. Basal nucleus of Meynert ○ Locus coeruleus v. Intralaminar nucleus of thalamus ○ Basal nucleus of Meynert v. Intralaminar nucleus of thalamus ○ PH v. FST ○ Substantia nigra v. Caudate nucleus • Exploratory pairs: Other 15 combinations of the pre-specified parcellations, other pairs of parcellations found to be anomalies by Infinitome program
Aim 2: Correlate cross-sectional dysfunction between LSBN parcellations with specific neuropsychological abnormalities in DLB Patients
Functional connectivity (FC) scores between pairs of LSBN parcellations (same primary pairs of interest as Aim 1).
Scores on neuropsychological tests: WMS-R Logical Memory Story A, Boston Naming Test Short, Category Fluency, WMS-R Digit Span Forward and Backward, ANART, RAVLT, Trails A/B, WMS-R Digit Symbol, Clock Drawing, NPI-Q, FAQ, ADAS-Cog 13

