
et al., 2018). There are connections to other brain regions including area or hub FST, which is involved in integrating information related to detail, motion, and form. Thus, our study will focus on pairwise functional connectivity between the seven parcellations listed in **Table 2**.

Table 2. Parcellations of Interest for Each DLB Core Symptom and Associated LSBN		
DLB Core Symptom	Associated Large Scale Brain Network	Parcellations of Interest
Cognitive fluctuations	Ascending brainstem norepinephrine tracts	Locus coeruleus, basal nucleus of Meynert, intralaminar nucleus of thalamus (Edlow et al., 2020)
Visual hallucinations	Inferior longitudinal fasciculus	Areas PH and FST (Pezzoli et al., 2017)
Parkinsonism	Ascending brainstem dopamine tracts	Substantia nigra, caudate nucleus (Young & Penney, 1984)

One potential challenge for functional imaging to this point is that brain parcellations (or distinct brain partitions) have been based on outdated models such as the Broadmann map from the 19th century (Zilles, 2018). In 2009, the Human Connectome Project (HCP) began one of the most ambitious neuroscientific initiatives to map the brain (Fox, 2018; Glasser et al., 2016). This project identified 379 functional areas of the brain and discovered 97 new regions that had never been previously described. This data has provided neuroscientists for the first time in history the ability to view the brain not merely as a structural entity, but as an individualized network system.

Figure 1: Infinitome Program – Removed for CT.GoV version

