Omniscient, a for-profit, Sydney, Australia-based company, created the cloud-based software Infinitome, a program that utilizes data from the HCP together with machine learning to analyze diffusion tensor and resting-state fMRI imaging data from remote sites (**Figure 1**). The foundation for this imaging tool is based upon the HCP atlas, which has also informed prior publications from our group, including the Connectomic Atlas of the Human Cerebrum (Baker, Burks, Briggs, Conner, et al., 2018). The Infinitome program creates a subject specific version of the Human Connectome Project Multimodal Parcellation (HCP-MMP1) atlas using diffusion tractography. Analytics are performed on both diffusion tensor imaging and rs-fMRI. Outlier detection using a tangent space connectivity matrix is performed by comparing results with a subset of 300 normal HCP subject fMRI samples to determine the range of normal correlations for each regions of interest in a LSBN. Abnormal connectivity is determined as a 3-sigma outlier for that correlation. The imaging protocol for rs-fMRI is limited to 15 minutes, enabling each study to be readily added on to structural MRI sequences. The program also provides automated image processing and analysis, thus simplifying the process of accessing imaging data and incorporating rs-fMRI into routine practice. By providing support for fMRI processing through a cloud-based server and incorporating normal control data from the HCP, this program addresses the challenges associated with the analysis and interpretation of rs-fMRI data. Thus, it has the potential to simplify the incorporation of rs-fMRI into clinical trials as a biomarker for neurodegeneration of vulnerable networks in DLB. Preliminary work has shown that connectomic analysis in AD subjects using this software is feasible and can detect functional anomalies involving regions of interest described by the HCP (Ren et al., 2020). Results from this proposal

will be applicable to both clinical practice and research where a diagnostic biomarker may impact either medical decision-making or enrollment into a clinical trial.

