8.2 POWER ANALYSIS OR STATEMENT OF PRECISION

In a one-way ANOVA, sample sizes of 19 DLB, 38 AD, and 38 CN achieve 80% power to detect differences among the means versus the alternative of equal means using an F test with a 0.01 significance level and assuming a common standard deviation within a group of 0.05. This is true for any set of group means with a standard deviation greater than or equal to 0.02, which we anticipate being able to achieve based on previous research. All significant brain connection couples in Franciotti's work had standard deviations of the group means greater than 0.06.

For post-hoc tests, group sample sizes of 19 DLB, 38 AD, and 38 CN patients achieve 81% power to reject the null hypothesis of equal means when the population mean difference is 0.05 with a standard deviation for both groups of 0.05 and with a significance level (alpha) of 0.010 using a two-sided two-sample equal-variance t-test.

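### Extra connection pairs may be chosen because they look abnormal between groups and then tested in the same 95 scans, with no correction for the pairs screened

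*Combined protocol and SAP*

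**What the plan says.** Section 8.1, Aim 1 Analysis, sets an order: the primary pairs first, then the other combinations of the seven parcellations, then an open category: "If additional, unexpected anomalies are present between groups, we will test them in an exploratory fashion to advance this novel field of study". The same paragraph states that "Bonferroni post hoc test will be used to correct for multiple comparisons", without defining the family. The Aim 2 paragraph of section 8.1 has a matching clause that admits further pairs if the connectivity analysis brings them up.

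Section 3 and Table 4 word the trigger differently. There the exploratory set includes "other pairs of parcellations found to be anomalies by Infinitome program". Section 2.1 describes how the software finds anomalies, namely by "comparing results with a subset of 300 normal HCP subject fMRI samples", and adds: "Abnormal connectivity is determined as a 3-sigma outlier for that correlation".

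The Updated A Priori SAP of 06 FEB 2024 describes Aim 1 as a one-way ANOVA on prespecified pairs, 8 primary and 22 exploratory. It does not list the 30 pairs or mention the anomaly rule. It correlates test scores only with the primary Aim 1 pairs, and it applies Holm only to the exploratory correlations of Aim 2.

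**The concern.** A test is valid when the hypothesis was fixed without sight of the data that test it. The section 8.1 sentence lets a pair in because the groups appear to differ and then tests it for that difference, with no hold-out sample, threshold or cap. Calling the test exploratory limits the claim but does not make the p-value valid.

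The study aims at a diagnostic imaging biomarker. Section 2.1 itself says that DLB has no defined pattern of network deterioration and that earlier studies disagree. In that setting, a nominally significant pair found by search in 19 DLB patients could be reported as a new DLB signature.

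**Working it through.** **Inputs.** Groups of 19 DLB, 38 AD and 38 CN, 95 scans in all (section 8.2). Seven parcellations (section 2.1, Table 2). The 379 areas, from "This project identified 379 functional areas of the brain" (section 2.1). The 3-sigma flag against external normal subjects (section 2.1). The 22 exploratory pairs (SAP update, Aim 1). No significance level is stated for the extra pairs or for the 22, so I assume 0.05 and also show 0.01 for the 22.

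**1. The plan's own figures.** The plan states no number of pairs searched. Its post hoc power reproduces: noncentrality 0.05 / (0.05 × √(1/19 + 1/38)) = 3.56 on 55 degrees of freedom, two-sided alpha 0.01, gives 80.9% against the stated 81%. The overall test was sized "using an F test with a 0.01 significance level and assuming a common standard deviation within a group of 0.05". Since 0.05/5 = 0.01, the level looks like Bonferroni over the five primary pairs of the protocol. That is an inference, but nothing suggests that it covers searched pairs. The prespecified count is also loose: seven parcellations give 7 × 6 / 2 = 21 pairs, and 21 − 5 = 16, where section 3 and Table 4 say 15.

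**2. Trigger is an observed group difference (section 8.1 wording).** If null pairs are screened at level s by the same ANOVA, and s is at least 0.05, the chance that a selected pair has p < 0.05 is 0.05/s. At s = 0.05 this is 100%. Tested at 0.01 after the same screen, it is 0.01/0.05 = 20%.

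**3. Trigger is the 3-sigma outlier flag (sections 2.1 and 3, Table 4).** A null simulation of 400,000 pairs, with standard normal values in groups of 19/38/38, gives these type I error rates at nominal 0.05 among flagged pairs:

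- outlier in any of the 95 subjects: 5.0%
- outlier in at least one DLB patient: 6.4%
- outlier in a DLB patient and in no AD or CN subject: 6.4%
- outliers in two or more DLB patients: 7.6%

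So circularity is small. These rates assume normal data and no scanner shift. That assumption is not secure, because the DLB scans come from one local scanner while the AD and CN scans come from a database.

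**4. How many null pairs are flagged.** The two-sided 3-sigma probability is 0.0027. The chance of at least one flag among 19 patients is 1 − (1 − 0.0027)^19 = 0.0501, assuming independence. About 5 of every 100 null pairs searched are therefore flagged, whatever the total. The upper bound is all pairs of 379 areas: 379 × 378 / 2 = 71,631. Then 71,631 × 0.0501 is about 3,600 flagged null pairs, of which 3,600 × 0.064, about 230, would have p < 0.05. Bonferroni over the full search would need 0.05/71,631 = 7.0 × 10⁻⁷.

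**5. The 22 exploratory pairs of the update.** Uncorrected at 0.05, the expected number of false positives is 22 × 0.05 = 1.1, and the family-wise error is 1 − 0.95^22 = 68% if the tests are independent. At 0.01 the figures are 0.22 and 1 − 0.99^22 = 20%. The Bonferroni threshold over 22 is 0.05/22 = 0.0023.

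**The case against.** The strongest reply is that the 2024 update has closed the route. It describes Aim 1 as a fixed set of 30 pairs called prespecified and mentions no software-flagged pairs. A closed count reads naturally as a replacement. This carries weight, but the update does not say that it replaces the rule in sections 3 and 8.1, and a reader holding both texts cannot tell which governs. For Aim 2 the reply largely succeeds: with correlations limited to the primary pairs, flagged pairs have no way in if the update supersedes the protocol sentence.

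Second, the documented software flag is an outlier against an external reference, not a contrast of the study groups. This stands, and it is why circularity cannot be asserted under every reading. It does not answer multiplicity.

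Third, if the protocol paragraph still applies, so does its Bonferroni correction. That is fair. It would be wrong to say that the protocol has no correction at all, but a correction with no stated family cannot be applied to an open-ended search.

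Fourth, these tests come last and are labelled exploratory, so no primary conclusion depends on them. This limits the consequence.

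**Conclusion.** The point holds in a limited form. The protocol allows data-selected pairs to be tested in the scans that selected them, and states no correction for the search. Under the section 8.1 wording the test is circular, fully so when the screen is at least as strict as the test. Under the software-flag wording the error per test is about 5 to 8% at nominal 0.05 (normal data, no scanner shift), and the defect is mainly uncontrolled multiplicity. For the 22 pairs of the update, the cost of no correction is 1.1 expected false positives and 68% family-wise error at an assumed 0.05, if independent.

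A reader might infer more, and the documents do not support it:

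- **That 71,631 pairs are searched.** No section says so. The figure is an upper bound, and section 2.1 speaks of regions of interest within a network, which may be far fewer.
- **That every such p-value is circular.** This depends on which trigger applies.
- **That the most extreme pairs will be ranked and picked.** The plan describes no such selection.
- **That the 22 pairs were chosen after the scans were seen.** The update calls its pairs prespecified. It is written in the past tense and does not say how or when they were chosen, so the claim can be neither confirmed nor refuted.

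**What to change.** - Reconcile sections 3 and 8.1 (with Table 4) with the 2024 update. Either withdraw the anomaly rule, or keep it and report any flagged pair descriptively, with an estimate and interval and no p-value or significance claim. If it is kept, say which trigger applies.
- If flagged pairs are to be tested, state the number of pairs searched and correct over all of them, by permuting group labels with a maximum-statistic or false-discovery correction.
- List the 22 exploratory pairs, say how and when they were chosen, and apply Holm or a false-discovery correction to them, in line with the Holm correction that the update uses for the exploratory correlations.
- Delete the sentence in the Aim 2 paragraph of section 8.1 that lets other pairs in, so that it agrees with the update.

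The cost is SAP wording, plus a permutation run only if flagged pairs are tested. The downside is fewer nominally significant exploratory pairs.
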